7.7.2 Secondary Efficacy Endpoints and Analyses

Secondary efficacy variables will be analysed in a descriptive manner. Summary statistics will be presented overall and by treatment group and an exploratory comparison will be performed between the two treatment groups. Analysis will be done for FAS and PP analysis set.

7.7.2.1 Key Auditory Verbal Learning Test (RAVLT) Score

RAVLT results of Recall List A [Total number of correct words], Recall List B [Number of correct words] and Final recall of List A scores [Number of correct words] will be analysed for each visit as actual values and change from Baseline. An exploratory ANCOVA will be performed on the change from Baseline (Week 0) to Week 12/EOT for comparison between the treatment groups, including treatment group as fixed effect, and the Baseline value as a covariate. The analysis described for primary efficacy analysis will be used for RAVLT data. Scoring details are given in Appendix 3.

7.7.2.2 Clinical Dementia Rating scale - Sum of Boxes (CDR-SOB) Score

CDR-SOB score (0 – 18) is a sum of all six items of CDR-SOB. CDR-SOB score will be analysed for each visit as actual values and change from Baseline. An exploratory ANCOVA will be performed on the change from Baseline (Week 0) to Week 12/EOT for comparison between the treatment groups, including treatment group as fixed effect, and the Baseline value as a covariate. The analysis described for primary efficacy analysis will be used for CDR-SOB data. Scoring details are given in Appendix 3.

7.7.2.3 Mini-Mental Status Examination (MMSE) Score

MMSE total score (0 - 30) is a sum of all 30 point questionnaire of MMSE. MMSE will be analysed for each visit as actual values and change from Baseline. An exploratory ANCOVA will be performed on the change from Baseline (Week 0) to Week 12/EOT for comparison between the treatment groups, including treatment group as fixed effect, and the Baseline value as a covariate. The analysis described for primary efficacy analysis will be used for MMSE data. Scoring details are given in Appendix 3.

7.7.2.4 Neuropsychiatric Inventory (NPI)

The NPI total score is calculated by multiplying the frequency and severity rates per domain (maximum score per domain is 12) and then calculating the total of all domains (total NPI-score minimum is 0 and maximum 144). Total distress score (0 – 60) will be summarized descriptively. Scoring details are given in Appendix 3.

Total NPI score, score by domain and total distress score will be analysed for baseline and last visit including change from Baseline. An exploratory ANCOVA will be performed on the change from Baseline (Week 0) to Week 12/EOT in the total NPI score for comparison between the treatment groups, including treatment group as fixed effect. Subgroup analyses will be performed for subjects with (score > 1) and without (score 0 to 1) symptoms at Baseline if warranted by the number of subjects in each treatment. The analysis described for primary efficacy analysis will be used for NPI data.

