15.2.3.6 Evaluation of Secondary Efficacy Variables

Secondary efficacy variables will be analysed in a descriptive manner. Summary statistics will be presented overall and by treatment group, and an exploratory comparison will be performed between the two treatment groups.

RAVLT: Results will be described for each visit as actual values and change from Baseline. An exploratory ANCOVA will be performed on the change from Baseline to Week 12/EOT for comparison between the treatment groups, including treatment group as fixed effect, and the baseline value as a covariate.

CDR-SOB: Results will be described for each visit as actual values and change from Baseline. An exploratory ANCOVA will be performed on the change from Baseline to Week 12/EOT for comparison between the treatment groups, including treatment group as fixed effect and the baseline value as a covariate.

MMSE: Results will be described for each visit as actual values and change from Baseline. An exploratory ANCOVA will be performed on the change from Baseline to Week 12/EOT for comparison between the treatment groups, including treatment group as fixed effect and the baseline value as a covariate.

NPI: Results will be described by domain for Baseline and last visit. An exploratory ANCOVA will be performed on the change from Baseline to Week 12/EOT for comparison between the treatment groups, including treatment group as fixed effect. Sub-group analyses will be performed for subjects with (score > 1) and without (score 0 to 1) symptoms at Baseline if warranted by the number of subjects in each treatment group and sub-group.

NTB – Executive Domain (COWAT and CFT): Results will be described for Baseline and last visit. An exploratory ANCOVA will be performed on the change from Baseline to Week 12/EOT for comparison between the treatment groups, including treatment group as fixed effect, and the baseline value as a covariate. In addition to the composite score, independent components will be analysed.

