7.7.1.1 ADCOMs/ADAS-Cog v14 score

ADCOMs, composite score (0 - 1.97) is derived from ADAS-Cog v14, CDR-SOB, and MMSE. ADAS-Cog v14 score is sum of all 14 items of ADAS-Cog v14. Scoring details for ADCOMs and ADAS-Cog v 14 score are given in Appendix 3.

For analysis of the primary efficacy variables, analysis of covariance (ANCOVA) model will be used to assess the change in ADCOMs/ADAS-Cog v14 score from Baseline (Week 0) to Week 12/EOT. The ANCOVA model will include treatment group as fixed effects and the Baseline value as a covariate.

The primary efficacy hypothesis is:

$$H_0: \mu_P \leq \mu_X$$

$$H_1: \mu_P > \mu_X,$$

where μ_P and μ_X denote the change from Baseline (Week 0) to Week 12/EOT in ADCOMs and ADAS-Cog v14 for the placebo and Xanamem™ treatment groups, respectively. Both tests will be performed at a type I error rate of 0.05 one-sided, with a priori hierarchical handling of multiplicity, based on the least squares means (LS means) for Week 12/EOT. LS means from the ANCOVA will be used to derive 90% and 95% confidence intervals. The primary efficacy analysis will not replace missing Week 12/EOT.

Unless otherwise specified, the ANCOVA will have the following characteristics:

- All subjects in the FAS will be included in the primary efficacy analysis as long as there are both Baseline and valid post-Baseline measurements at Week 12/EOT available.
- The response variable will be the change in ADCOMs score from Baseline (Week 0) to Week 12/EOT visit. Only post-Baseline measurements collected on the EOT will be considered response values.
- The following covariate will be used in the models:
 - Baseline ADCOMs score

- Treatment group
- The following SAS statements will be employed:

```
proc mixed data=xxxx ;
    class <treatment group>;
    model < change ADCOMs score> = <baseline ADCOMs score>
    <treatment group> ;
    lsmeans <treatment group>/ diff cl alpha=0.05;
    lsmeans <treatment group>/ diff cl alpha=0.10;
    ods output lsmean=xxx diffs=xxx;
run;
```

Baseline ADCOMs score, as well as observed and change from Baseline values at post-Baseline visits, will be summarized descriptively.

The analysis described above will be repeated for ADAS-Cog v14. Also analysis will be repeated on PP analysis set for supportive evidence.

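### The protocol gives the NPI ANCOVA no baseline covariate and SAP 7.7.2.4 supports two different models; state that baseline NPI is a covariate

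*SAP*

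**What the plan says.** **Protocol 15.2.3.6.** The entries for RAVLT, CDR-SOB, MMSE and NTB each give an ANCOVA of the change to Week 12/EOT with treatment group and baseline. The NPI entry stops at treatment group and moves straight on to subgroups: "including treatment group as fixed effect. Sub-group analyses will be performed". It does not refer back to the primary model.

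**SAP 7.7.2.4 (NPI).** The model sentence, for the total NPI score, has the same single term: "including treatment group as fixed effect. Subgroup analyses will be performed for subjects with". The paragraph then closes with "The analysis described for primary efficacy analysis will be used for NPI data".

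**SAP 7.7.1.1 (primary analysis).** The model referred to is explicit: "The ANCOVA model will include treatment group as fixed effects and the Baseline value as a covariate". The SAS code there carries the baseline term as well.

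**Neighbouring SAP sections.** RAVLT, CDR-SOB and MMSE have both the covariate and the cross-reference, for example "and the Baseline value as a covariate. The analysis described for primary efficacy analysis will be used for CDR-SOB data" and "and the Baseline value as a covariate. The analysis described for primary efficacy analysis will be used for MMSE data". In SAP 7.7.2.5 the NTB total is also given baseline. The sentence on the NTB components (COWAT and CFT) names no covariate, and that section too refers back to the primary analysis.

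**Baseline data.** NPI is collected at Baseline and Week 12 (Protocol Table 1 and 11.1.1.6).

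**SAP section 10.** No change from the protocol's methods is recorded.

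**The concern.** In the protocol, NPI stands out from the scales listed beside it, and no reason is given. A change-score model with treatment alone is an unadjusted comparison of mean changes, even though it is called an ANCOVA. In the SAP the difficulty is of another kind: one sentence gives a model without baseline, and the last sentence of the paragraph points to a model with it. Two programmers could fit different models and each cite the SAP.

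Two things are at stake. One is precision if the treatment-only model is run. The other is that the choice between the models stays open and could be made after results are seen. The ambiguity also reaches the interim analysis, because SAP 9.5 lists NPI and sends its analysis to section 7.7.

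**Working it through.** **1. The plan's own figure.** The documents state no standard deviation, correlation or sample size for NPI, so there is no NPI figure to reproduce. The stated sample size rests on ADAS-Cog v14 (Protocol 15.1: difference 2, SD of change 5, one-sided 5%, power 80%):

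- n per arm = 2 × (5/2)² × (1.645 + 0.842)² = 12.5 × 6.185 = 77.3, so 78.
- Randomised = 156 / 0.90 = 173.3, so 174.

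Both reproduce, and NPI does not enter either of them.

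**2. The model terms side by side.**

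| Endpoint | Protocol 15.2.3.6 | SAP model sentence | SAP refers to primary model |
|---|---|---|---|
| RAVLT, CDR-SOB, MMSE | treatment + baseline | treatment + baseline | yes |
| NTB total | treatment + baseline | treatment + baseline | yes |
| COWAT, CFT components | to be analysed, no terms given | ANCOVA, no terms given | yes |
| NPI | treatment | treatment | yes |

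The protocol plainly leaves the term out for NPI. The SAP is inconsistent within one paragraph.

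**3. Can the SAP text settle it?** The ANCOVA characteristics in SAP 7.7.1.1 apply unless something else is specified. The NPI model sentence can be read as specifying something else, and the cross-reference can be read as overriding it. Section 10 does not decide the matter. Taken at face value it favours the protocol's treatment-only model. But the same SAP has four sensitivity analyses in 7.7.1.1 where Protocol 15.2.3.5 has two, and section 10 does not record that either. Its silence is weak evidence about any single model.

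**4. Precision if treatment-only is run.** Assume equal variance s² at Baseline and Week 12 and correlation r between them.

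- Variance of the change score: 2s²(1 − r).
- Residual variance after adjusting for baseline: s²(1 − r²).
- Ratio, adjusted to unadjusted: (1 − r²) / [2(1 − r)] = (1 + r)/2.

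The standard error scales with the square root of this ratio. As an illustration only, since NPI is not powered, the last column takes an unadjusted comparison with 80% power at one-sided 0.05 and gives the adjusted power, Φ[(1.645 + 0.842)/√((1+r)/2) − 1.645].

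| r (assumed) | variance ratio | SE ratio | SE reduction | adjusted power |
|---|---|---|---|---|
| 0.3 | 0.65 | 0.806 | 19% | 92.5% |
| 0.5 | 0.75 | 0.866 | 13% | 89.0% |
| 0.7 | 0.85 | 0.922 | 8% | 85.4% |
| 0.9 | 0.95 | 0.975 | 2.5% | 81.8% |

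**5. Chance imbalance.** Under the same assumptions, an unadjusted change score passes on (1 − r) of any chance baseline difference, with opposite sign; at r = 0.5 that is half. One standard error of baseline difference is s√(2/78) = 0.16s at 78 per arm. At about 25 per arm, as at the interim, it is s√(2/25) = 0.28s.

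**The case against.** The strongest reply is that the SAP already prescribes baseline adjustment. The closing sentence sends NPI to the primary analysis, the list of terms before it is not said to be exhaustive, and an ANCOVA without a covariate would be a misnomer. That is a fair reading and suggests a dropped phrase. It is not the only reading, though. The same closing sentence follows scales whose model sentence does name baseline, so it looks like standard text rather than a substitute for listing terms. The protocol entry has no such sentence at all.

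Two stronger claims are tempting, and the documents do not support either. A reader might infer that the SAP definitely fits NPI without baseline; the cross-reference prevents that. A reader might also infer that NPI is the only efficacy model without a named baseline term; the COWAT and CFT component sentence names none either.

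Three further points stand on the other side:

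- Under randomisation the unadjusted comparison of changes is unbiased on average. Imbalance matters only for the particular sample.
- Both documents plan NPI subgroups by baseline symptoms (score above 1 against 0 to 1) if numbers allow, so baseline severity is not ignored, although this does not replace a covariate.
- The gain depends on an unstated r and on equal variances, and it is small if r is high. No NPI data are given, so an argument from skewness cannot be documented.

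**Conclusion.** The point holds as a plain omission in Protocol 15.2.3.6 and an internal inconsistency in SAP 7.7.2.4 that section 10 does not resolve. If the treatment-only model is run, the standard error of the NPI difference is larger than it need be: over r from 0.3 to 0.9, adjustment would reduce it by between about 19% and 2.5%. That range rests on the assumed r and on equal variances at the two visits. If the primary model is run, no precision is lost and only the wording needs correcting.

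The consequence is limited. Both documents treat secondary endpoints descriptively with exploratory comparisons, and NPI lies outside the confirmatory hierarchy. A reader should not infer bias in the NPI estimate, or any effect on the ADCOMs and ADAS-Cog v14 tests, the 78 per arm or the 174 randomised. What is gained is some precision and a single model fixed in advance.

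**What to change.** Before unblinding, rewrite the model sentence in SAP 7.7.2.4 so that it names treatment group and baseline NPI total score, which makes it agree with the closing cross-reference. Align the NPI entry in Protocol 15.2.3.6, or, if the protocol is not to be amended again, record the added covariate in SAP section 10. While that text is open, name the baseline of each component for COWAT and CFT in SAP 7.7.2.5, so that they do not depend on the cross-reference alone. State which NPI model was used if the interim analysis has already been run.

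The cost is one model term and one degree of freedom. Baseline NPI is already scheduled for collection, so no new data are needed.

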7.7.2.5 Neuropsychological Test Batteries (NTB) – Executive Domain

Total NTB score is the sum of ‘Total correct response’ of Category Fluency Test (CFT) and ‘Total number of correct words’ of Controlled Oral Word Association – Test (COWAT). Each score (‘Total correct response’ of CFT and ‘Total number of correct word’ of COWAT) will also be analysed. Those results will be analysed for Baseline and last visit including change from Baseline. An exploratory ANCOVA will be performed on the change from Baseline (Week 0) to Week 12/EOT in the NTB total score for comparison between the treatment groups, including treatment group as fixed effect, and the Baseline value as a covariate. In addition to the composite score, the change from Baseline (Week 0) to Week 12/EOT in independent components will be analysed with ANCOVA for COWAT and CFT - total correct responses score. The analysis described for primary efficacy analysis will be used for NTB- executive domain data. Sensitivity analysis with adding sites as covariate will be performed in FAS population. Site will be pooled as same to the primary efficacy endpoint. Scoring details are given in Appendix 3.

7.8 Safety Endpoints and Analyses

All safety endpoints will be summarized for safety analysis set with actual treatment group received. The following are the safety endpoint variables that will be summarized.

- Clinical safety laboratory values for haematology, biochemistry and urinalysis
- AEs, SAEs, and AESIs
- ECG
- NFM
 - NTSS-6
 - TCNS

- NCV and amplitude of peripheral motor and sensory nerves
- CSSRS
- Physical examination
- Vital signs

7.8.1 Adverse Events

Any detrimental change in the subject's condition collected from after signing the ICF and up to completion of the 4-week Follow-up period after the last administration of study drug, should be considered an AE. Any new SAEs occurring up to 60 days after the last administration of study drug should be reported.

Treatment-emergent adverse events (TEAEs) are those AEs which worsen in severity on or after date of first administration of study drug or with onset date on or after first administration of study drug.

AEs with missing start dates, but with stop dates either overlapping into the treatment period or missing, will be considered TEAEs. A TEAE with missing drug-relationship will be considered as related.

All AEs will be coded by SOC and PT using the latest version of MedDRA. Incidences of TEAEs will be tabulated by SOC and PT. Incidences of TEAEs will also be presented by maximum severity, seriousness, AESI and drug-related. Subjects who are temporary or permanently discontinued from treatment and discontinued from study will be summarized by SOC and PT in a separate table. Subjects are counted only once in each SOC, and only once in each PT category.

The following tables will be developed for summarizing AEs.

- Overall summary of TEAEs: it includes number of TEAEs, subjects with any TEAE, subjects with any SAE, subjects with any severe TEAEs, subjects with any drug-related TEAEs, subjects with any AESI, subjects with TEAEs leading to temporary or permanently treatment discontinuation, subjects with TEAEs leading to study discontinuation.
- Summary of TEAEs by SOC and PT
- Summary of serious TEAEs by system organ class and preferred terms
- Summary of TEAEs by system organ class, preferred terms and maximum severity
- Summary of drug-related TEAEs by system organ class, preferred terms
- Summary of Treatment-emergent AESI by system organ class and preferred terms

- Summary of TEAEs leading to temporary or permanent discontinuation of study drug by system organ class, preferred terms
- Summary of TEAEs leading to study discontinuation by system organ class, preferred terms

All AEs, AESI, SAEs and deaths will be listed.

7.8.2 Clinical Safety Laboratory Parameters

Descriptive statistics for absolute value and absolute change from Baseline [only for continuous results parameters, otherwise display percentage change from Baseline] for protocol specified laboratory parameters of biochemistry, haematology and urinalysis will be presented for Baseline (Week 0) to EOT (Week 12) by treatment group and overall. International System of Units (SI units) will be used for the analysis. The abnormality in laboratory parameters will be summarized by treatment group.

Values outside the normal range (N) will be categorized as H (above the normal range) or L (below the normal range) based on the reference range of the Safety Laboratories. Shift tables will be presented showing the number of subjects per treatment group with N, H or L at the Baseline (Week 0) to EOT (Week 12). Laboratory test results will be listed by including laboratory blood tests, which are to only be performed at screening and abnormal values outside normal ranges will be flagged.

The following laboratory test parameters will be summarized:

Laboratory Test	Parameters
Haematology	Haemoglobin, Haematocrit, Platelet count, Red blood cell count, White blood cell count and differential, Basophils, Eosinophils, Monocytes, Neutrophils and Lymphocytes
Biochemistry	Alkaline Phosphatase, Alanine Aminotransferase (ALT), Aspartate Aminotransferase (AST), Gamma-glutamyl transpeptidase, Phosphorous, Potassium, Uric acid, Bilirubin (total), Protein (total), Creatinine, Follicle-stimulating hormone [Females only. To be taken only if there is clinical concern about the subject's menopausal status], Human chorionic gonadotrophin [Pregnancy test on women of childbearing potential only]
Urinalysis	Urate crystals, phosphate crystals, bilirubin crystals, blood, clarity, colour, glucose, ketones, leukocytes, protein, squamous epithelial cells, trans. epithelial cells, triple phosphate crystals, Microscopic examination [Performed only if required, based on urinalysis results]

Metabolic indicators	Glucose, fasting, Cholesterol, Triglycerides, High-density lipoprotein-cholesterol, Low-density lipoprotein-cholesterol, HbA1c, Very Low-density lipoprotein (VLDL) Cholesterol
----------------------	---

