9.2.2 Risk/Benefit and Ethical Assessment

Xanamem™'s mechanism of action suggests a main role on hippocampal function, which may improve amnesic symptoms that are the main symptoms in subjects of mild AD. Furthermore, Xanamem™ may slow the progression of amyloid plaque deposition in the brain. Therefore, Xanamem™ has the potential for both symptomatic and disease-modifying effects in subject with mild AD.

Xanamem™ is an inhibitor of the 11β -HSD1 enzyme. Compounds which inhibit 11β -HSD1 are intended to affect the intracellular cortisone-cortisol balance, resulting in altered glucocorticoid action. It is therefore expected that AEs seen following the administration of Xanamem™ may be related to effects on glucose and fatty acid metabolism, or loss of suppression of innate immunity. In addition, inhibition of 11β -HSD1 results in enhanced cortisol clearance and potentially a compensatory increase in ACTH and cortisol secretion to maintain normal cortisol levels. As a result, ACTH-dependent secretion of adrenal androgens may be increased.

To date, Xanamem™ has an acceptable safety profile: in the MAD study²², all treatment-emergent AEs (TEAEs) were either mild or moderate in intensity. A total of 6/24 (25.0%) subjects reported at least one TEAE possibly related to study drug, whilst all the other TEAEs were reported as unrelated or unlikely to be related to study drug.

Of the five TEAEs considered to be moderate in intensity, one event of diarrhoea (20 mg UE2343) and one event of headache (35 mg UE2343) were considered as possibly related to study drug. The other moderate TEAEs were all unrelated or unlikely to be related to study drug. The laboratory parameters were within normal range and no clinically significant abnormalities were recorded. In the subsequent fed-fasted study²² in 12 subjects, the most commonly reported TEAE by preferred term was "Abnormal dreams", with a total of

five events reported by 5/12 (41.7%) subjects. These were considered possibly related to study drug (two events under fed conditions, one under fasted conditions and two across both the fed and fasted period), all mild in intensity and resolved.

Overall, there were no clinically significant abnormalities noted in nerve conduction studies for any of the subjects in the MAD cohorts.

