9.3.2 Exclusion Criteria

A subject will NOT be eligible for this study if ANY of the following criteria apply:

1. Clinically significant abnormalities in vital signs (blood pressure, heart rate, respiration rate and oral temperature), as determined by the investigator.
2. Clinically significant abnormal haematology, biochemistry and urine examination values, as determined by the investigator. Additionally, abnormal liver and renal function and Vitamin B12 levels below lower threshold may impact cognitive function. The following values will have an alert flag on the laboratory report and are specifically excluded:

- a) Vitamin B12 < 176 pg/mL
- b) Haemoglobin < 11 g/dL for females and < 12 g/dL for males
- c) Aspartate aminotransferase > 3 x upper limit of normal (ULN)
- d) Alanine aminotransferase > 3 x ULN
- e) Serum creatinine > 2 x ULN
- f) Urine benzodiazepines when positive: One re-test will be allowed in cases where the subject's intake of benzodiazepines is within the allowed dose. Re-tests must be performed within 7 days of the last benzodiazepine dose prior to the Baseline visit. A positive re-test for urine benzodiazepines is exclusionary.

Re-testing of laboratory parameters that requires a confirmatory value within the screening period will be permitted in an effort to find all possible well-qualified subjects. The most current result prior to randomisation is the value by which study inclusion will be assessed, as it represents the subject's most current, clinical state. Consultation with the ICON MM is advised, to identify whether repeat testing of any particular parameter is acceptable and clinically relevant.

3. Has had a significant systemic illness or infection within the past 4 weeks prior to randomisation, as determined by the investigator.
4. Clinically significant neurological disease other than AD, such as (but not limited to) Parkinson's disease, multi-infarct dementia, Huntington's disease, normal pressure hydrocephalus, brain tumour, progressive supranuclear palsy, seizure disorder, subdural haematoma, multiple sclerosis or a history of significant head trauma followed by persistent neurologic deficits or known structural brain abnormalities.
5. Subjects with clinical evidence of peripheral neuropathy or historical evidence of clinically significant nerve conduction abnormalities. Clinical evidence of neuropathy is defined as:

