- The subject is unable to tolerate their prescribed study drug per protocol.
- Subject has evidence of drug-induced liver injury or any other drug-induced injury (such as thrombocytopenia), detected in ongoing safety monitoring of laboratory results.
- Subject is confirmed to be pregnant.

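### The SAP's laboratory shift tables use only low/normal/high from Baseline to EOT, so no planned laboratory table counts large AST, ALT or creatinine rises by arm

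*SAP*

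**What the plan says.** SAP 7.8.2 sets the rule for haematology, biochemistry and urinalysis: "Values outside the normal range (N) will be categorized as H (above the normal range) or L (below the normal range"). The layout follows: "Shift tables will be presented showing the number of subjects per treatment group with N, H or L at the Baseline (Week 0) to EOT". The section also plans descriptive statistics for values and change from Baseline, a by-group summary of abnormality that it does not define further, and listings with out-of-range flags. Protocol 15.2.3.7 likewise refers only to the normal range. Neither document has a table in multiples of ULN, a toxicity grading, a marked-abnormality threshold or a joint transaminase and bilirubin count.

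Eligibility is wider than the normal range. Criterion 2 in Protocol 9.3.2 opens with "Clinically significant abnormal haematology, biochemistry and urine examination values, as determined by the investigator" and then lists specific limits, among them "Aspartate aminotransferase > 3 x upper limit of normal (ULN"), "Alanine aminotransferase > 3 x ULN" and "Serum creatinine > 2 x ULN".

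The protocol treats laboratory safety as a live question. Section 9.5 lists as a ground for withdrawal "Subject has evidence of drug-induced liver injury or any other drug-induced injury (such as thrombocytopenia"). Section 9.2.2 expects AEs that "may be related to effects on glucose and fatty acid metabolism". Safety laboratory samples are scheduled at Screening, Baseline, Weeks 4, 8 and 12, and Follow-up (Protocol Table 1).

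**The concern.** A shift table is the usual place to see whether more subjects worsened on one arm than on the other. With a single class above the reference limit, it registers only a crossing of that limit. Three kinds of event are lost or blurred:

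- A subject who enters above ULN and worsens stays in H-to-H. So does a subject who improves but remains above ULN.
- A subject who enters normal is N-to-H whether the EOT value is just above the limit or many times above it.
- A peak at Week 4 or Week 8 that resolves is not in the table. For a subject who was H at Baseline and is back in range by EOT, the table shows H-to-N, an apparent improvement.

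At stake is the between-arm reading of hepatic and renal safety, both in the final report and in the interim analysis, which takes its laboratory methods from SAP 7.8 (SAP 9.5). Primary efficacy, sample size and type I error are untouched.

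**Working it through.** The plan states no figure on this point that could be reproduced. The check applies the SAP rule to values that eligibility permits.

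**Inputs.** Class rule: H if value / ULN > 1 (SAP 7.8.2). Permitted entry values: AST and ALT up to 3 × ULN, creatinine up to 2 × ULN (Protocol 9.3.2). Randomised per arm: 87; expected completers per arm: 78 (Protocol 15.1). The on-treatment values below are illustrations, not predictions.

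| Analyte | Baseline (× ULN) | EOT (× ULN) | EOT / Baseline | SAP cell |
|---|---|---|---|---|
| ALT or AST | 1.5 | 8 | 8 / 1.5 = 5.3 | H-to-H |
| ALT or AST | 2 | 10 | 10 / 2 = 5.0 | H-to-H |
| ALT or AST | 3 | 20 | 20 / 3 = 6.7 | H-to-H |
| ALT or AST | 3 | 2 | 2 / 3 = 0.7 | H-to-H |
| ALT or AST | 0.8 | 8 | 8 / 0.8 = 10.0 | N-to-H |
| ALT or AST | 0.8 | 1.01 | 1.01 / 0.8 = 1.3 | N-to-H |
| Creatinine | 1.5 | 3 | 3 / 1.5 = 2.0 | H-to-H |
| Creatinine | 2 | 4 | 4 / 2 = 2.0 | H-to-H |

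A rise of 6.7-fold and a fall to 0.7 of Baseline share one cell. A rise to 1.01 and a rise to 8 × ULN share another. This follows from the rule alone and needs no assumption about frequency.

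**How many subjects.** The documents do not give the share who are H at Baseline. Assume 2% to 20% for a given analyte:

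- 0.02 × 87 = 1.7 and 0.20 × 87 = 17.4, so about 2 to 17 per arm as randomised.
- 0.02 × 78 = 1.6 and 0.20 × 78 = 15.6, so about 2 to 16 per arm among completers.

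Far fewer would have a large rise. If 1% to 10% of those subjects (assumed) rose above 5 × ULN, the expected number per arm is between 87 × 0.02 × 0.01 = 0.02 and 87 × 0.20 × 0.10 = 1.7.

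**Timing.** The shift table uses two time points. SAP Appendix 2 defines the EOT window as Days 81 to 89. Subjects who stop early have EOT assessments only where possible (Protocol Table 1, footnote 2), and the SAP does not say whether an early-termination sample enters the EOT column. SAP 5.1 generally leaves unscheduled measurements out of descriptive analyses, so a repeat sample drawn because a value was high would normally appear only in a listing.

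**Check of the remedy.** With edges at 1 and 3 × ULN, the first three ALT/AST rows move from the >1–3 band to the >3 band, the improving row stays in >1–3, and the last two separate into >3 and >1–3. With edges at 1 and 2 × ULN, both creatinine rows move from >1–2 to >2.

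**The case against.** The strongest reply is that the loss is confined to one display.

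- SAP 5.1 includes minimum and maximum in the summary statistics, and SAP 7.8.2 applies these to values and to change from Baseline by arm. An ALT of 8 × ULN at a scheduled visit would probably be its arm's maximum. Protocol 15.2.3.7 calls for results at each visit, which would cover Weeks 4 and 8.
- Out-of-range values are listed by subject.
- Protocol 12.1.1.2 makes a laboratory abnormality an AE if it meets an SAE criterion, leads to discontinuation, interruption or dose change, or is thought reportable by the investigator. SAP 7.8.1 tabulates TEAEs by severity, seriousness and discontinuation.
- The DSMB reviews unblinded laboratory data (Protocol 15.2.4).
- Investigator-judged significant abnormalities are excluded at entry, so the group with a raised Baseline is probably small.
- The protocol promised tables based on normal ranges, and the SAP delivers them.

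All of this stands. A reader might infer from the H-to-H cell that the plan conceals a serious liver or renal signal, or that no by-arm output could reveal one. The documents do not support that, for the reasons just listed. Nor do they support reading the SAP as departing from the protocol, or any particular share of subjects with a raised Baseline.

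What remains is narrower. A maximum shows one extreme value, not how many subjects had one. A listing has to be counted by hand. The AE tables depend on investigator action or judgement and are not graded by size of excursion. The SAP already does more for ECGs: its 7.8.3 shift tables separate clinically significant abnormalities and cover all scheduled post-dose visits.

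**Conclusion.** The point holds as a weakness of the by-arm laboratory summary. Under the stated rule, worsening in subjects already above ULN is tabulated as no shift, N-to-H does not grade the rise, and a resolved mid-study peak is absent from the shift table. No planned laboratory table counts such rises by arm.

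The classification result rests only on the SAP rule and the entry limits. The size does not: about 2 to 17 of 87 per arm in the H Baseline row assumes a share of 2% to 20%, and the number with a large rise is likely to be very small. That makes this a cheap improvement that should be made, not a defect that threatens the trial's conclusions. A few cases per arm is nevertheless the situation in which a count by arm is more informative than a mean or a three-class shift.

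**What to change.** In SAP 7.8.2, keep the existing tables and add:

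1. A by-arm table of Baseline category against worst post-Baseline value, in multiples of ULN. Use all post-Baseline visits, including early-termination and unscheduled samples, and state that this overrides the general exclusion of unscheduled values in SAP 5.1. Take the band edges from the protocol's own limits: AST and ALT ≤1, >1–3 and >3 × ULN, with at least one higher band; creatinine ≤1, >1–2 and >2 × ULN, with a higher band. The higher edges are for the sponsor to choose.
2. A by-arm count of subjects with AST or ALT >3 × ULN together with total bilirubin above ULN.

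Say in the text that these are reporting bands and not stopping rules.

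I would not add a count of glucose or lipid values that rise within H. Without a minimum rise it would count trivial fluctuation, and SAP 7.10.1 already gives change from Baseline by arm for these analytes. Haemoglobin bands are not needed for this point either.

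As a minor clarification, SAP 7.8.2 should summarise non-continuous urinalysis results by category frequency, as SAP 5.1 does for categorical data. A percentage change from Baseline has no meaning for results such as colour or clarity.

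The cost is one or two extra tables from data already collected, with small counts in most bands. No visit, sample or procedure changes.
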